2.2. Study Endpoints

2.2.1. Primary Endpoint:

- Objective radiographic response (ORR), as measured by modified Response Assessment in Neuro-Oncology (RANO) criteria

2.2.2. Secondary Endpoints:

- Safety and tolerability will be assessed by monitoring frequency, duration, and severity of adverse events (AEs) through physical examinations, by evaluating changes in vital signs, and through clinical laboratory evaluations.
- OS, defined as the time from date of enrollment until death from any cause
- PFS, defined as the time from date of enrollment until the earliest date of disease progression (as determined by modified RANO criteria) or death due to any cause

2.2.3 Exploratory Endpoints:

- Comparison of the following immunocorrelative assays in subjects treated with INCMGA00012 + INCAGN01876, with or without SRS:
 - Multiplex immunohistochemistry on tumor tissue for CD4/8 T cell infiltration, Foxp3+ Treg infiltration, and PD-1/PD-L1 expression
 - Tumor cell and immune cell GITR expression by a validated immunohistochemistry stain
 - Flow cytometry/mass cytometry in tumor tissue and peripheral blood for T cell and monocyte phenotyping
 - RNA-Seq on tumor tissue for PD-1/PD-L1 and GITR expression, T cell- and interferon- γ -related gene expression, and cell-cycle-related gene expression
 - T cell receptor sequencing in tumor tissue and peripheral blood for assessment of TCR clonal diversity
- Association between the above tumor tissue and peripheral blood-based markers of immune activation, tumor genetic mutations, and clinical outcomes of OS, PFS, and ORR
- PK parameters for INCAGN01876 in patients with glioblastoma
- Detection of anti-drug antibodies (ADA) against INCAGN01876

3 INVESTIGATIONAL PLAN

3.1. General Design

This is a single-center, phase II, open label study evaluating the efficacy and safety of the combination of INCMGA00012, INCAGN01876 and SRS for patients with recurrent GBM.

The overall study population will be broken down into two cohorts: Cohort A (N=16) and Cohort B (N=16). Subjects for whom surgical resection is not clinically indicated at the time of study

screening will be enrolled into Cohort A (non-surgical cohort). Subjects for whom surgical resection is clinically indicated at the time of study screening will be enrolled into Cohort B (surgical cohort).

The first 6 subjects enrolled onto the study must be enrolled onto Cohort A and will be enrolled in two groups of 3 subjects (i.e., a “3+3” design) as part of a safety run-in period. After enrollment of the first 3 subjects, enrollment is put on hold until all of the first 3 subjects have completed the safety monitoring period (completion of SRS and one cycle of INCMGA00012 and INCAGN01876). If only 0-1 of the first 3 subjects experiences a criterion for study drug discontinuation, as defined in [Section 5.7, Study Drug Discontinuation Criteria](#), then the next 3 subjects will be enrolled. If 2 of the first 3 subjects experience a criterion for study drug discontinuation, the study will be paused for reconsideration of the dosing and schedule of investigational agents.

Of the first 6 subjects enrolled during the safety run-in, if 3 or greater subjects experience a criterion for study drug discontinuation, then the study will be paused for reconsideration of the dosing and schedule of investigational agents. If only 0-2 of the first 6 subjects enrolled during the safety run-in experience a criterion for study drug discontinuation, then enrollment to both cohorts A and B will commence uninterrupted.

If at any point during the safety run-in a stopping rule is met and the dose/schedule of investigational agents is changed, the safety run-in will start over again with another 6 patients. If Cohort A has reached enrollment of 12 subjects and the criteria to move beyond the safety run-in phase has still not yet been met (i.e., at least 6 patients have been treated at the same dose/schedule and only 2 or fewer have experienced a criterion for study drug discontinuation), the trial (including Cohort B) will be terminated due to intolerability of the study regimen.

If at any point during the safety run-in a stopping rule is met and the dose/schedule of investigational agents is changed, and the safety-run in phase is then successfully completed at the new dose/schedule, 16 additional subjects will be enrolled in Cohort A at the new dose/schedule to achieve the desired sample size of 16 subjects that are evaluable for the study’s primary endpoint. Thus, the total sample size for Cohort A could potentially be more than 16 subjects (e.g., 6 subjects are enrolled in the initial safety run-in and 3 of them experience a toxicity requiring study drug discontinuation; an additional 6 subjects are then enrolled at the new dose/schedule that has been decided upon, and this time the safety run-in is completed successfully with only 1 subject discontinuing study drug due to toxicity; we would then enroll 10 additional subjects at the current dose/schedule of study drugs to achieve 16 evaluable subjects treated at the final dose/schedule; the total sample size for cohort A in this example would be 22 subjects).

Cohort B will not start enrollment until the safety run-in phase has been successfully completed.

Details of treatment administered in each cohort are provided below in [Section 3.1.2, Study Intervention Phase](#).

[figure not shown]

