GGT: gamma-glutamyl transferase

GI: Gastrointestinal

GITR: Glucocorticoid-induced TNFR family related protein

GLP: Good Laboratory Practice

Gy: Gray

h: hour

HBV: Hepatitis B virus

HCV: Hepatitis C virus

HCG: Human chorionic gonadotropin

hfRT: hypofractionated radiotherapy

Hgb: Hemoglobin

HIV: Human immunodeficiency virus

IB: Investigator's brochure

ICHL International Conference for Harmonisation of Technical Requirements for
Pharmaceuticals for Human Use

IDH: Isocitrate dehydrogenase

IHC: immunohistochemistry

IMRT: Intensity-modulated radiation therapy

INR: International normalized ratio

IRB: institutional review board

IU: International Units

IUD: intrauterine device

IV: Intravenous (ly)

kDa: kilodaltons

Kg: Kilograms

L: liter

LDH: Lactate dehydrogenase

LFTs: liver function tests

Mg: Milligrams

MGMT: O6-Methylguanine-methyltransferase

mL: milliliter

mM: millimolar

mRANO: modified Response Assessment in Neuro-Oncology Criteria

MRI: Magnetic Resonance Imaging

MTD: maximal tolerated dose

NA: Not available

NOAEL: no-observed-adverse-effect-level

ORR: Objective response rate

OS: Overall survival

PAD: pharmacologically active dose

PCR: polymerase chain reaction

PD: Progressive disease

PD-1: programmed cell death protein 1

PD-L1: programmed death-ligand 1

PFS: Progression-free survival

PFS-6mo: Progression-free survival rate at 6 months

P-gp: p-glycoprotein

PK: Pharmacokinetic (s)

PR: Partial response

PRO: Patient reported outcomes

PS: Performance status

PT: Prothrombin time

PTT: Partial thromboplastin time

QD: once a day

Qtc: corrected QT interval

RANO: Response Assessment in Neuro-Oncology Criteria

RNA seq: Ribonucleic acid sequencing

RT: Radiation therapy

SAE: Serious adverse event

SD: Stable disease

SMC: safety monitoring committee

SRS: stereotactic radiosurgery

T_{1/2}: half-life

TEAS: treatment emergent adverse events

TK: toxicokinetic

TMZ: Temozolomide

TRAE: treatment related adverse event

TTFields: Tumor-treating fields

UADE: Unanticipated Adverse Device Experience

ULN: upper limit of normal

VEGF: Vascular endothelial growth factor

V_{ss}: volume of distribution at steady-state

WHO: World Health Organization

WOCBP: Women of child bearing potential

WT: Body weight

Table of Contents

TABLE OF CONTENTS	8
STUDY SYNOPSIS	12
1 BACKGROUND	17
1.1 INTRODUCTION	17
1.2 DISEASE BACKGROUND.....	17
1.3 NAME AND DESCRIPTION OF INVESTIGATIONAL DRUGS.....	18
1.3.1. INCMGA00012	18

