- Objective radiographic response (ORR), as measured by modified Response Assessment in Neuro-Oncology (RANO) criteria

Secondary Endpoints:

- Safety and tolerability will be assessed by monitoring frequency, duration, and severity of adverse events (AEs) through physical examinations, by evaluating changes in vital signs, and through clinical laboratory evaluations.
- OS, defined as the time from date of enrollment until death from any cause PFS, defined as the time from date of enrollment until the earliest date of disease progression (as determined by modified RANO criteria) or death due to any cause

Exploratory Endpoints:

- Comparison of the following immunocorrelative assays in subjects treated with INCMGA00012 + INCAGN01876, with or without SRS:
 - Multiplex immunohistochemistry on tumor tissue for CD4/8 T cell infiltration, Foxp3+ Treg infiltration, and PD-1/PD-L1 expression

- Tumor cell and immune cell GITR expression by a validated immunohistochemistry stain
- Flow cytometry/mass cytometry in tumor tissue and peripheral blood for T cell and monocyte phenotyping
- RNA-Seq on tumor tissue for PD-1/PD-L1 and GITR expression, T cell- and interferon- γ -related gene expression, and cell-cycle-related gene expression
- T cell receptor sequencing in tumor tissue and peripheral blood for assessment of TCR clonal diversity
- Association between the above tumor tissue and peripheral blood-based markers of immune activation, tumor genetic mutations, and clinical outcomes of OS, PFS, and ORR
- PK parameters for INCAGN01876 in patients with glioblastoma
- Detection of anti-drug antibodies (ADA) against INCAGN01876

Sample Size, Power,

Statistical Analysis: The total sample size for this trial is 32 subjects.

- 16 subjects will comprise the non-surgical arm, Cohort A, which serves as the cohort for the primary study endpoint analysis (subjects do not have clinical indication for surgical resection).
- 16 subjects will comprise the surgical arm, Cohort B, which is the exploratory arm for correlative studies (subjects have clinical indication for surgical resection).
- Once a 3+3 safety run-in phase had been completed in Cohort A, the two cohorts will enroll simultaneously.

Cohort A (N=16):

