In both surgical sub-arms, within 7 days of enrollment the subject will receive a single dose of the investigational systemic agent(s) according to the sub-arm to which he/she is assigned. In sub-arm # 1 (INCMAG00012 + INCAGN01876 + SRS), within 3 to 7 days following the neoadjuvant doses of the systemic study drugs, the subject will receive SRS, administered over the course of 3 consecutive business days (8 Gy x 3 fractions, one fraction per day, total dose 24 Gy). Subjects may receive 3 fractions every other day (non-consecutively) for logistical reasons relating to COVID-19. Within 7-14 days following administration of the study drug(s) (surgical sub-arms # 2) or within 7-14 days following SRS (surgical sub-arm # 1), the subject will undergo maximal safe surgical resection of the tumor. Following surgery, the subject will then resume systemic therapy with BOTH investigational agents INCMGA00012 and INCAGN01876 (regardless of which of the two sub-arms the subject was assigned to). The systemic agents should be started as soon as the investigator feels the subject has recovered adequately from surgery, but must be restarted within 5 weeks (35 days) from the date of surgery. Subjects will continue on combined systemic treatment (INCMGA00012 500 mg IV every 4 weeks and INCAGN01876 300mg IV every 2 weeks) until disease progression, unacceptable AEs, or for 2 years, whichever occurs first.

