5.8 Management of Study Drug Toxicities

5.8.1. Supportive care for Immune-Related Adverse Events (irAEs)

GITR represents an important immune control receptor. It is anticipated that combining GITR agonism PD-1 inhibition could cause more frequent, more severe, and/or new immune-related toxicities compared to the well-described immune-related toxicity for single agent PD-1 inhibition ([Brahmer et al, J Clin Oncol 2018](#)). For this reason, a variety of measures are included to mitigate these potential risks. These measures are consistent with published guidelines for immune-related AEs associated with anti-PD-1 drugs, but are meant to apply to any suspected immune-related AEs from other immuno-oncology agents such as the combination of INCMGA00012 and INCAGN01876

Immune-related AEs may be defined as an AE of unknown etiology, associated with drug exposure and consistent with an immune phenomenon. Immune-related AEs may be predicted based on the nature of the INMGA0012 and INCAGN01876 compounds, their mechanism of action, and the extensive reported experience with immunotherapies that have a similar mechanism of action. Special attention should be paid to AEs that may be suggestive of potential irAEs. An irAE can occur shortly after the first dose or several months after the last dose of treatment.

If an irAE is suspected, efforts should be made to rule out neoplastic, infectious, metabolic, toxin or other etiologic causes before labeling an AE as an irAE. Subjects who develop a \geq Grade 2 irAE should be discussed immediately with the principal investigator.

Recommendations for management of *specific* immune-mediated AEs such as pneumonitis, enterocolitis, hepatitis, dermatitis, neuropathies, endocrinopathies, and other immune-mediated AEs, and are based on recently published guidelines for the management of immunotherapy-related toxicities that have recently been published by the National Comprehensive Cancer Network (NCCN) in partnership with the American Society of Clinical Oncology (ASCO), available here:

https://www.nccn.org/professionals/physician_gls/pdf/immunotherapy.pdf

and here:

<http://ascopubs.org/doi/10.1200/JCO.2017.77.6385>

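### The trial-level toxicity count stops with the Cohort A run-in, so 26 of 32 planned subjects, including all 8 given drugs plus SRS before resection, enrol with no stated safety boundary

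*Combined protocol and SAP*

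**What the plan says.** The Synopsis plans two cohorts of 16: "The total sample size for this trial is 32 subjects". Section 3.1 places the run-in wholly in the non-surgical cohort: "The first 6 subjects enrolled onto the study must be enrolled onto Cohort A". The first three are observed through "completion of SRS and one cycle of INCMGA00012 and INCAGN01876" before the next three enter.

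Two limits apply. The first is "If 2 of the first 3 subjects experience a criterion for study drug discontinuation, the study will be paused". The second is a pause at 3 or more of the first 6. Section 3.1 ties both to the run-in, and a changed regimen restarts it, up to 12 Cohort A subjects. After 0 to 2 of 6, "then enrollment to both cohorts A and B will commence uninterrupted". Cohort B cannot open earlier.

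For Cohort B sub-arm 1, Section 3.1.2 gives both drugs, then SRS, and "within 7-14 days following SRS (surgical sub-arm # 1), the subject will undergo maximal safe surgical resection of the tumor". Section 5.8.1 anticipates that the drug combination "could cause more frequent, more severe, and/or new immune-related toxicities" than PD-1 inhibition alone, and notes that such events can appear months after the last dose.

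Later provisions are of other kinds: discontinuation of individual subjects (5.7), descriptive safety summaries (8.2.2), SAE notification within 24 hours (9.3.2), termination by the sponsor on emerging data with no threshold (3.4), and a reference to a monitoring plan (11.1). The abbreviations list "SMC: safety monitoring committee", but no section gives that committee a task.

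**The concern.** Six subjects followed for one cycle give little information on tolerability, and after them no cumulative count is compared with anything. Three features sharpen this.

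- **Timing.** One of the main Section 5.7 criteria is toxicity that fails to improve within 12 weeks of the last dose. The run-in window is SRS plus one 28-day cycle, so the run-in can miss events of the kind it is meant to count.
- **Population.** No run-in subject has surgery. The sequence of drugs, SRS and early resection is never examined by a counting rule. The preoperative SRS evidence in Section 1.5.2 comes from brain metastases.
- **Pre-specification.** Safety is a secondary objective. Without a stated trigger, any decision to pause after subject 6 is made ad hoc.

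At stake is whether a poorly tolerated regimen that passes the run-in by chance would prompt a review before most subjects have been enrolled.

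**Working it through.** **Plan's own figure.** Section 8.2.1 asks for 16 evaluable subjects to test 5% against 25% with one-sided alpha 0.05 and 80% power. An exact binomial test that rejects at 3 or more of 16 has alpha 0.0429 and power 0.8029, while n = 15 gives power 0.764. The 16 reproduces. With Cohort B the total is 16 + 16 = 32. The documents give no operating characteristics for the run-in.

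**Subjects outside the rule.**
- Base case: 32 − 6 = 26 (81%), made up of 10 in Cohort A and 16 in Cohort B. Eight of the 16 are in sub-arm 1.
- One restart after 6 subjects: Cohort A becomes 22 and the total 22 + 16 = 38. The run-in covers 12, leaving 38 − 12 = 26 (68%).

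**Probability of passing one run-in.** Let p be the true rate of meeting a criterion in the window, and X1 and X2 the counts in the two groups of three. The text names 2 of 3 but not 3 of 3; I take 3 of 3 as a pause too.

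P(pass) = P(X1=0)·P(X2≤2) + P(X1=1)·P(X2≤1)

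- p = 1/3: (8/27)(26/27) + (12/27)(20/27) = 448/729 = 0.6145
- p = 0.40: 0.216 × 0.936 + 0.432 × 0.648 = 0.482
- p = 0.50: 0.125 × 0.875 + 0.375 × 0.500 = 0.297

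At 40%, 26 × 0.40 = 10.4 later subjects would be expected to meet a criterion, with no rule counting them. A passing 2 of 6 has an exact 95% interval of 4.3% to 77.7%; 0 of 6 has an upper limit of 45.9%.

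**A boundary consistent with the run-in.** With a uniform prior, x events in n subjects give a Beta(x+1, n−x+1) posterior. P(rate > 1/3) is 0.593 at 1/3, 0.889 at 2/3, 0.571 at 2/6 and 0.827 at 3/6. A threshold of 0.80 therefore reproduces both run-in limits. Extended:

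| n | one below | boundary |
|---|---|---|
| 12 | 5: 0.759 | 6: 0.897 |
| 18 | 7: 0.721 | 8: 0.854 |
| 24 | 9: 0.696 | 10: 0.822 |

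The choice is not unique. Thresholds from about 0.60 also reproduce 2/3 and 3/6, and at 0.60 to 0.65 the boundaries are 5/12, 7/18 and 9/24.

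**Operating characteristics after a passed run-in.** Start from the distribution of the count in 6 given a pass. Add a Binomial(6, p) count to reach each of 12, 18 and 24, removing paths that reach the boundary. The rate is assumed equal in both cohorts.

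| True rate | Pause, 6/12, 8/18, 10/24 |
|---|---|
| 20% | 1.2% |
| 25% | 4.4% |
| 1/3 | 19% |
| 40% | 39% |
| 50% | 72% |
| 60% | 93% |

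With 5/12, 7/18 and 9/24 the pause probability at 1/3 is 37%.

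**Adding a separate 2/3 and 3/6 check on the first Cohort B subjects.** By simulation (400,000 trials, equal rates, alternating enrolment after subject 6), total pauses rise to about 15% at 20%, 24% at 25% and 43% at 1/3. Detection becomes 61% at 40%, 84% at 50% and 96% at 60%.

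**The case against.** The limited gating is a reasoned choice. Both drugs are given at recommended phase 2 doses, 56 subjects had already received this GITR antibody dose with nivolumab (Section 1.3.2.2), and the preoperative SRS reports cited in Section 1.5.2 found no added morbidity. This stands as rationale. It does not test the three-part regimen or the surgical sequence in recurrent GBM.

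A reader might infer that safety goes unwatched after subject 6. The documents do not support that. Subject-level stopping runs throughout, SAEs reach the sponsor and Medical Director within 24 hours, and the sponsor may terminate on emerging data. The monitoring plan is a separate document, and a committee boundary could be in it. What is missing from the documents reviewed is a stated trial-level limit.

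A reader might also infer that a rate of 1/3 breaches the protocol's own tolerability limit. The protocol states no such rate; 1/3 is read off the fact that 2 of 6 passes. Both the 1/3 and the 0.80 are reviewer assumptions, and equally compatible thresholds give tighter boundaries.

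Finally, the run-in counts any Section 5.7 criterion, including confirmed progression, withdrawn consent and pregnancy. A later check restricted to toxicity counts a different event, and a longer window would count a larger cumulative rate. This stands, and it is why the event and window must be written down.

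**Conclusion.** The gap holds as a design weakness that should be closed. The count in Section 3.1 ends with the run-in, and 26 later subjects, including all of Cohort B, enrol with no stated boundary. The run-in alone is a weak screen: it passes true rates of 1/3, 40% and 50% with probability 61%, 48% and 30%.

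The head counts and pass probabilities are exact for a single run-in with independent subjects, but the true rates are illustrative. The pause and detection figures rest further on the assumed 1/3 limit and 0.80 threshold, a common rate in both cohorts, and one fixed counting window. They give the chance that a pause is triggered. Without an enrolment hold, some subjects will enter while counts mature. A pooled count also dilutes an excess confined to the 8 subjects in sub-arm 1.

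**What to change.** Add one paragraph to Section 3.1:

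- A pooled rolling count over both cohorts, starting with the six run-in subjects at the final schedule and with no enrolment hold. Pause for review when 6 of 12, 8 of 18 or 10 of 24 subjects have met a toxicity-based Section 5.7 criterion.
- A definition of the event, including how toxicity attributed to SRS is counted. Section 9.2 already records attribution to drug and/or SRS, whereas the persistent-toxicity criterion in 5.7 refers to the study drugs.
- One fixed counting window per subject. The operating characteristics should be recalculated if the expected rate over that window differs from the one-cycle rate.
- Who reviews a pause. If this is the committee in the abbreviations, give it that task; if the monitoring plan already holds a boundary, state it here.
- The basis, labelled as an assumption: posterior P(rate > 1/3) of at least 0.80 with a uniform prior, noting that lower thresholds match the run-in equally well.

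The cost is a running count of data already collected and a small chance of an unneeded pause: 1.2% at a true rate of 20% and 4.4% at 25%. The paragraph sets no dose and no rule for individual subjects.

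A separate 2/3 and 3/6 check on the first Cohort B subjects is for the sponsor to weigh. It is the only part aimed directly at the surgical sequence, but with it total pauses rise to about 15% at 20%, 24% at 25% and 43% at 1/3.

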5.5 Study drug Administration

5.5.1 Administration of INCMGA00012

INCMGA00012 is administered as an IV infusion over 60 minutes for the first infusion. If well tolerated, it may be administered over 30 minutes for subsequent treatments. On days when both study drugs are due to be administered, INCMGA00012 study product is administered first prior to administration of INCAGN01876. The only dose of INCMGA00012 used for this study is 500mg. There is no dose escalation or reduction. A 1-hour observation period is recommended after the INCMGA00012 infusion prior to beginning the INCAGN01876 infusion.

Infusion-related reactions (including anaphylaxis or cytokine release syndrome) may be associated with the administration of therapeutic antibodies. Of 199 prior study participants who have received infusions of INCMGA00012 in Study INCMGA 0012-101, 5 participants have experienced 1 infusion-related reaction each (see IB). This does not exceed the expected incidence of IRRs for the PD-1 inhibitor class. Infusion-related reactions were observed in Study INCMGA 0012-101 regardless of whether prophylaxis was administered; therefore, routine prophylaxis is not recommended. Secondary prophylaxis is recommended for participants who have experienced IRRs to INCMGA00012. Participants who experience life-threatening infusion reactions should not be retreated with INCMGA00012. Infusions reactions should be managed according to the guidelines in [Section 5.8.2](#).

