5.5.2 Administration of INCAGN01876

INCAGN01876 is administered as an IV infusion over 60 minutes for the first infusion. If well tolerated, it may be administered over 30 minutes for subsequent treatments. On days when both study drugs are due to be administered, INCMGA00012 study product is administered first prior to administration of INCAGN01876. The only dose of INCAGN01876 used for this study is 300mg. There is no dose escalation or reduction. A 1-hour observation period is recommended after the INCMGA00012 infusion prior to beginning the INCAGN01876 infusion.

Preclinical assessments used to evaluate theoretical safety concerns with INCAGN01876 eliciting adverse proinflammatory infusion reactions did not induce cytokines that in vivo would be predictive of CRS in participants, so the risk of significant infusion reactions is considered to be low. For participants who have an infusion reaction associated with administration of INCAGN01876, signs and symptoms would usually develop during or shortly after drug infusion

and generally resolve completely within 24 hours of completion of infusion. Infusions reactions should be managed according to the guidelines in [Section 5.8.2](#).

5.6 Concomitant Medications:

1) Following start of study drug, concomitant medications and therapies deemed necessary for the supportive care and safety of the subject are allowed, provided their use is documented in the subject records and on the appropriate case report form. This includes corticosteroids of any dosage for the management of brain edema related to the tumor and/or study drugs. The administration of any other anticancer agents including chemotherapy and biologic agents (such as bevacizumab) is NOT permitted. Similarly, the use of other concurrent investigational drugs is not allowed.

2) List of medications that are prohibited during this study:

- Any anticancer medications, including chemotherapy or biologic therapy other than the study medications
- Any immunological-based treatment for any reason, with the exception of corticosteroids
- Any investigational agents other than INCAGN01876 and INCMGA00012
- Radiation therapy other than the SRS (8Gy x 3 fractions) administered as part of this protocol
 - Live vaccines. Examples include but are not limited to measles, mumps, rubella, varicella/zoster, yellow fever, rabies, Bacillus Celmette-Guerin (BCG), and typhoid. Intranasal influenza vaccines are not allowed.

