and described in detail in **Appendix 1** with specific application to this protocol. These recommendations include management of the toxicity itself, as well as guidance for dose interruptions/delays of the investigational agents. There are no dose reductions or dose escalations permitted for either investigational agent.

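### The safety run-in may change the dose or schedule, but the dosing sections fix both without exception, and Cohort B's regimen after a restart is not linked to the run-in result

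*Combined protocol and SAP*

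**What the plan says.** **Run-in (Section 3.1).** The first six Cohort A subjects enter in two groups of three. There are two triggers. The first, which covers the schedule as well as the dosing, begins: "If 2 of the first 3 subjects experience a criterion for study drug discontinuation, the study will be paused for reconsideration of the dosing and". The second applies to the six together: "if 3 or greater subjects experience a criterion for study drug discontinuation, then the study will be paused for reconsideration". The event counted is any Section 5.7 criterion for stopping study drug. After a trigger, if "a stopping rule is met and the dose/schedule of investigational agents is changed, the safety run-in will start over again with another 6 patients". When the repeated run-in succeeds, "16 additional subjects will be enrolled in Cohort A at the new dose/schedule". Sections 3.2, 3.5 and 8.2.1(a) rely on the same idea, because they define the 16 evaluable Cohort A subjects by one common or final dose and schedule.

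**Dosing text.** Section 5.5.1: "The only dose of INCMGA00012 used for this study is 500mg. There is no dose escalation or reduction". Section 5.5.2: "The only dose of INCAGN01876 used for this study is 300mg", again with no escalation or reduction. Section 5.8.1, at the end of the immune-related toxicity text: "There are no dose reductions or dose escalations permitted for either investigational agent". The synopsis and Section 1.5.1 give 500 mg every 4 weeks and 300 mg every 2 weeks. Section 3.1.2 repeats those figures for continued treatment in both cohorts. None of these places makes an exception for a run-in change.

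**Cohort B.** It opens only after the run-in has succeeded, and it closes with the whole trial if the run-in cannot be completed within 12 Cohort A subjects (Section 3.1). Under Section 3.5 its recruitment ends when 16 subjects have had study drug and surgery, with no dose or schedule condition.

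**The concern.** The run-in is the only numeric trial-level toxicity rule in the documents, and a possible change of regimen is built into it. If the rule is triggered, site staff and pharmacy would be working from a protocol in which one section provides for a new dose or schedule and others say that only the existing one is used. The primary analysis set also depends on the answer, since Section 8.2.1(a) selects subjects by the final dose and schedule.

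Cohort B adds a second gap. Section 3.1 carries a new regimen forward for Cohort A only and sends the reader to Section 3.1.2 for treatment details in each cohort. There, the only milligram doses and intervals written for Cohort B are those in force before any change. Up to 16 planned subjects would enter with no statement of which text applies to them.

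**Working it through.** **1. The plan's own figure.** For 5% against 25%, one-sided 0.05 and 80% power, the exact binomial design with 16 subjects and success at 3 or more responses has a type I error of 0.0429 and power of 0.8029. The stated 16 is reproduced, and this point leaves it unchanged.

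**2. Passages side by side.**

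| Type of change | Provided for in | Conflicts with |
|---|---|---|
| Dose | 3.1 (relied on in 3.2, 3.5, 8.2.1(a)) | 5.5.1, 5.5.2; fixed doses in synopsis, 1.5.1, 3.1.2 |
| Interval only | 3.1 (same) | Fixed intervals in synopsis, 1.5.1, 3.1.2; not 5.5 or 5.8.1, which speak of dose |

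The 5.5 wording refers to doses used for the study, so reading it as a rule about individual subjects does not remove the conflict. Section 5.8.1 is weaker support. It follows guidance on interruptions and delays for toxicity and can be read as a per-subject rule.

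**3. Link to the run-in result.** Cohort A is tied to it in 3.1, 3.2, 3.5 and 8.2.1(a). Cohort B is tied to it nowhere as regards dose or schedule. For Cohort B's preoperative step, Section 3.1.2 specifies a single dose but no milligram amount. The 500 mg and 300 mg figures there govern treatment after surgery.

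**4. How often the path could be reached.** The documents give no Section 5.7 event rate, so let p be an assumed true rate, the same for every subject and independent between subjects. The text names 2 of the first 3 as a trigger and does not mention 3 of 3; I treat both as a stop.

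- Stop in the first three: S1 = 3p²(1−p) + p³.
- Stop at six after passing three: S2 = (1−p)³·p³ + 3p(1−p)²·[3p²(1−p) + p³]. That is, no events followed by 3 of 3, or one event followed by 2 or 3 of 3.
- The first run-in fails with probability S1 + S2.

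For p = 0.20: S1 = 0.096 + 0.008 = 0.104; S2 = 0.512 × 0.008 + 0.384 × 0.104 = 0.0441 − 0.0001 = 0.0440; the sum is 0.148.

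| p | S1 | S2 | First run-in fails |
|---|---|---|---|
| 5% | 0.0073 | 0.0011 | 0.8% |
| 10% | 0.0280 | 0.0075 | 3.6% |
| 20% | 0.1040 | 0.0440 | 14.8% |
| 30% | 0.2160 | 0.1045 | 32.1% |
| 40% | 0.3520 | 0.1659 | 51.8% |

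These are chances of a pause. The contradiction takes effect only if the pause then leads to a change, so they are upper limits for that first step.

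**The case against.** The strongest reply is that the stated response to a trigger is a pause for reconsideration, which nothing forbids. No replacement regimen is prespecified, so any change would have to be written later, and Section 1.1 requires sponsor and IRB approval of an amendment for any change to the protocol. That amendment could update 3.1.2 and 5.5. This stands in part: the conflict can be cured in time. But Section 3.1 mentions no amendment and presents the restart as part of the existing design, so the text should not depend on it.

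A reader might infer that Cohort B would be opened at the regimen that had just failed. The documents do not support that. Section 3.1.2 fixes Cohort A's regimen in the same terms, yet 3.1 plainly lets Cohort A move, so those terms cannot by themselves lock Cohort B. Holding Cohort B until the run-in succeeds, and ending it with the trial if the run-in does not, suggests that it was meant to follow the cleared regimen. What remains is that this is not written.

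The event rate may also be low. Section 1.3.2.2 reports 4 participants with dose-limiting toxicities among 56 given INCAGN01876 300 mg every 2 weeks with nivolumab. Taking p = 4/56 = 7.1%, S1 + S2 = 0.0146 + 0.0030, or about 1.8%. The proxy is imperfect: there was no radiosurgery, and the Section 5.7 list is not the same as a dose-limiting toxicity. It is still a reason to show low rates as well as high ones.

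**Conclusion.** Wrong as written, and it should be corrected. A dose change under Section 3.1 cannot coexist with Sections 5.5.1 and 5.5.2, and an interval change cannot coexist with the fixed schedules in Sections 1.5.1 and 3.1.2. Cohort B's regimen after a restart has no link to the run-in result, and the only one written for it is the starting regimen.

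The contradiction rests on the text alone. Its practical weight depends on an unknown event rate: the first run-in fails with probability 0.8% to 51.8% over assumed rates of 5% to 40%, given independent subjects and 3 of 3 counted as a stop. It would also be too strong to say that the plan bars its own response to toxicity. Pausing and terminating remain open, and 5.5 restricts dose, not interval. No sample-size or power figure changes.

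**What to change.** Reconcile the synopsis and Sections 1.5.1, 3.1, 3.1.2, 3.2, 3.5, 5.5.1, 5.5.2, 5.8.1 and 8.2.1(a) so that they give one answer to each of four questions:

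- Can the run-in change the dose, the schedule, both or neither?
- Does the only-dose wording in 5.5, and the sentence in 5.8.1, apply to the whole study or to individual subjects?
- Does a run-in change need an amendment under Section 1.1 before enrolment resumes?
- Which dose and schedule text governs Cohort B after a restart?

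The sponsor decides the clinical rule; no dose or rule is proposed here. While 3.1 is open, also settle a separate mismatch. It calls for 16 additional subjects after a successful restart, but its own example adds 10 (6 + 6 + 10 = 22, the maximum in Section 3.5), whereas 16 would give 6 + 6 + 16 = 28.

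The cost is wording in about ten places, with no added subjects or procedures and no change to the planned sample size.
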